## **7. RATIONALE AND BACKGROUND**

### **7.1. Rationale for the Current Study**

An increased risk of death and a higher incidence of serious adverse events (SAEs, predominantly infectious events) among subjects receiving idelalisib in combination with standard regimens compared to the control groups were observed in three Phase 3 studies evaluating treatment in first-line CLL and early-line iNHL patient populations by an independent data monitoring committee. The European Commission (EC) was notified of these findings and a review of these data was conducted by the Pharmacovigilance Risk Assessment Committee (PRAC) under Article 20 of Regulation (EC) No 726/2004. This review assessed the impact of these findings on the risk-benefit balance of Zydelig (idelalisib) in the approved EU indications. The PRAC review concluded that the risk-benefit profile for idelalisib remained positive for approved indications, with some updates to the indication and introduction of warnings and precautions in the Summary of Product Characteristics (SmPC) for risk minimization measures to minimize the risk of serious infections.

The risk-benefit balance of idelalisib monotherapy for the treatment of patients with follicular lymphoma (FL) that are refractory to 2 prior lines of treatment was considered to remain positive provided that the agreed risk minimization measures are applied. However, as no controlled study was conducted in this indication, the PRAC required Gilead to collect additional safety data in patients with refractory FL in order to better describe the safety profile of idelalisib in this population.

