## **9. RESEARCH METHODS**

### **9.1. Study Design**

A retrospective cohort study enrolling patients who were or are being treated with idelalisib for refractory FL according to the product information and treatment guidelines in routine clinical practice after the country specific approval date.

Patient's data will be collected from the date of treatment initiation with idelalisib until 6 months after treatment discontinuation.

The study design allows for both retrospective and prospective data to be collected. The start of data collection is defined as the entry of the first patient into the eCRF. In the data analysis, any data prior to the start of the study will be considered retrospective. Any data after that date will be considered prospective.

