## 9.7. Data Analysis

Categorical variables will be summarized descriptively by number and percentage of patients in each categorical definition including 95% confidence intervals. Continuous variables will be summarized descriptively by mean, standard deviation, median, lower quartile, upper quartile, minimum and maximum.

Multivariate Poisson regression analyses will be used to estimate rates of ADRs and SADR, adjusted for potential confounders (demographics, baseline disease assessment, medical history, treatment history, treatment changes; see section 9.3).

Multivariate Cox Proportional Hazard analyses will be used to model time-to-event data, and time to ADRs, SADR and AESIs.

Kaplan Meier curves will be used to illustrate time-to-event analyses.

Special focus will be given to the differences in retrospective and prospective data collection. Although not by intention, data might be collected differently in retrospect compared to patient's data that will be collected prospectively. Retrospective patients will be recruited through systematic search of the sites' patient data management system, whereas prospective data will be collected from those patients prescribed idelalisib after the start of the study. Behavioral changes of the site staff after the initiation of the study might play a role in differential data collection. Thus, missing data for the retrospective data might be an issue. Stratified analyses will be conducted to account for this potential bias.

The extent of missing data in the study will be described and tabulated. Imputation methods will be used to account for missing values in the dataset for those variables used in multivariate modeling (demographics, baseline disease assessment, medical history, treatment history) and changes in idelalisib treatment following the current ENCePP guidelines (Methodological Standards in Pharmacoepidemiology: Section 5.3. Handling of missing data;

[http://www.encepp.eu/standards\\_and\\_guidances/methodologicalGuide5\\_3.shtml](http://www.encepp.eu/standards_and_guidances/methodologicalGuide5_3.shtml) {Rubin 1987}, {Moons 2006}, {Welch 2014}. Multiple imputation by chained equations (MICE) as sequential regression multiple imputation will be used handling of missing data {Azur 2011}. Using MICE, missing values are imputed based on the observed values for a given individual and the relationships within the data for other participants.

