Stratified analyses will be taken into consideration to account for potential behavioral changes of the site staff after the initiation of the study that might introduce bias between retrospective and prospective data collection. These stratified analyses also account for the fact that less documentation might be available in data collected retrospectively.

Patterns of missing data will be determined using the methodology outlined by Chen {Chen 1999}. Here, it has to be determined if the "Missing At Random" (MAR) criterion is fulfilled. If the assumptions of MAR or missing completely at random (MCAR) are met then a multiple imputation approach will be used. If this assumption doesn't hold, a full case or regression approach may be used.

Multiple imputation by chained equations (MICE) also referred to as sequential regression multiple imputation, is a validated statistical method for the handling of missing data {Azur 2011}. Using MICE, missing values are imputed based on the observed values for a given individual and the relationships within the data for other participants.

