### **10.3. Informed Consent**

Gilead will collect informed consents for patients being identified prospectively. Informed consent will not be collected for deceased patients or patients identified retrospectively, unless specifically required by an appropriate ethics committee or required by country National Data Protection Laws, for a participating centre.

All data used in this study will be anonymized and collected in an eCRF with a unique subject identifier for each patient by each participating centre. In case the IEC or HREC requires a written informed consent to be obtained the investigator will be responsible for obtaining written informed consent from each prospective patient participating in this study after adequate explanation of the aims, methods, and objectives, and alternatives of the study prior to study participation and before collection of data. The investigator must utilize the most current IEC or HREC approved consent form for documenting written informed consent. Each informed consent will be appropriately signed and dated by the subject or the subject's legally authorized representative and the person conducting the consent discussion, and also by an impartial witness if required by IEC or HREC or local requirements.

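### Sections 9.1 and 9.7 define retrospective and prospective differently, and 9.1's single study-wide cut date counts data abstracted after the fact at later-starting sites as prospective

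*Protocol*

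**What the plan says.** **Rule by calendar date.** Section 9.1, repeated in the synopsis, gives a rule for the analysis: "any data prior to the start of the study will be considered retrospective. Any data after that date will be considered prospective". The start is one date for the whole study: "The start of data collection is defined as the entry of the first patient into the eCRF".

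**Rule by patient.** Section 9.7 describes the two groups by person. On one side, "Retrospective patients will be recruited through systematic search of the" sites' patient data systems. On the other, "prospective data will be collected from those patients prescribed idelalisib after the start of the study".

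**A third usage.** Section 10.3 turns on how the patient is identified: "Gilead will collect informed consents for patients being identified prospectively".

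**Purpose of the strata.** Section 9.7 gives the reason: "Behavioral changes of the site staff after the initiation of the study might play a role in differential data collection". Section 9.9 adds that retrospective documentation may be thinner. Section 9.7 and the synopsis commit to the stratified analyses; 9.9 is softer: "Stratified analyses will be taken into consideration to account for potential behavioral changes of the site staff after the initiation of the study".

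**Site start.** Section 10.2 bars an investigator from screening or collecting data before local ethics approval is documented. Section 9.2 lists 13 countries.

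**The concern.** The two rules classify different things. Section 9.1 classifies a piece of data by its date; 9.7 classifies a person by route of identification and prescription date. They disagree on every patient who started before the cut and was still under observation after it.

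The disagreement has consequences elsewhere in the protocol. Section 6 schedules an interim report on the retrospective data for Q1 2019, and the two rules put different person-time and events into it. Under 9.8 and 9.10.1.1, on-site review is confined to patients who consented, and 10.3 generally seeks consent only from those identified prospectively. Data after the cut from an unconsented patient already on drug are therefore prospective under 9.1 but have no source verification.

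The study-wide date also misses the bias it is meant to address. Staff behaviour changes when a site starts, not when the first patient is entered somewhere else. If under-recorded data are filed as prospective, the strata look more alike than they are, and a real recording gap can go unseen.

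**Working it through.** **The protocol's own figure.** The only computed figure nearby is the study size of 300 in 9.5. With n = 1.96² × p(1−p)/d², the three table columns (3.2%/0.02, 5.2%/0.025, 7.6%/0.03) give 297.5, 303.0 and 299.7. The figure reproduces, and this point does not depend on it.

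**The rules side by side**

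| Case | Section 9.1 | Section 9.7 |
|---|---|---|
| Started before the cut, observed beyond it | Split at the cut | Not in the prospective group; retrospective if found by record search |
| Started after the cut, before the site's own start | Prospective | Unclear: the record-search clause makes the patient retrospective, the prescription-date clause prospective |
| Started after the site's own start | Prospective | Prospective |

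**Size of the disagreement (row 1).** Inputs from 9.5 and 9.1: median treatment 8 months, 6 months of follow-up after stopping, about 3 years before the cut (R = 36 or 39 months) and 30 months after it. Assumptions: treatment starts spread evenly, and treatment either fixed at 8 months or exponential with median 8 (mean m = 8/ln 2 = 11.54 months).

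Let G(v) be the mean time observed within v months of starting. Per patient starting each month:

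- Person-time after the cut from patients starting after it: I = ∫ G(v) dv from 0 to 30.
- All person-time after the cut: P = ∫ G(v) dv from R to R + 30.
- All person-time: T = ∫ G(v) dv from 0 to R + 30.
- Share classed differently = 1 − I/P. In patient-years of 300: 300 × (P − I)/T.

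For a fixed observation time d, I = 30d − d²/2 and P = 30d, so the share is d/60.

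| Observation time | R | I | P | T | Share | Of 300 patient-years |
|---|---|---|---|---|---|---|
| Fixed 8 | 36 | 208.0 | 240.0 | 496.0 | 13.3% | 19.4 |
| Fixed 8 | 39 | 208.0 | 240.0 | 520.0 | 13.3% | 18.5 |
| Fixed 8 + 6 | 36 | 322.0 | 420.0 | 826.0 | 23.3% | 35.6 |
| Fixed 8 + 6 | 39 | 322.0 | 420.0 | 868.0 | 23.3% | 33.9 |
| Exponential | 36 | 222.9 | 340.8 | 629.0 | 34.6% | 56.2 |
| Exponential | 39 | 222.9 | 342.0 | 663.5 | 34.8% | 53.9 |
| Exponential + 6 | 36 | 322.4 | 517.1 | 938.0 | 37.6% | 62.3 |
| Exponential + 6 | 39 | 322.4 | 519.2 | 990.5 | 37.9% | 59.6 |

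The range is 13% to 38%. With the 6-month follow-up that 9.1 prescribes, it is 23% to 38%.

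**Size of the late-site problem under 9.1.** The protocol gives no activation dates, so a lag L of 3 to 12 months after the first eCRF entry is assumed. With person-time spread evenly over the 30 months, the mislabelled share of that site's prospective stratum is L/30: 3/30 = 10%, 6/30 = 20%, 9/30 = 30%, 12/30 = 40%. Exponential treatment times change these by less than one percentage point.

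**The case against.** The best defence is that 9.1 governs. Its rule is expressly for the data analysis, while the sentences in 9.7 explain how patients are found and why recording might differ. On that reading, the 13% to 38% measures a clash of wording, and splitting a spanning patient by date is sound practice. This stands in part: 9.1 is usable. But 9.7 is the analysis section and says something else, and the late-site problem arises under 9.1 itself.

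A reader might also infer more than the protocol supports:

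- *That chart abstraction in the prospective stratum is itself an error.* It is not. Medical records are the primary source throughout (9.4). The issue is abstraction after the fact, before the site was taking part.
- *That a patient treated before a late site opens is prospective under both rules.* This is clear only under 9.1. The record-search clause in 9.7 would make that patient retrospective.
- *That stratification is the only safeguard.* Identical variables (9.3), a standard eCRF and training (9.9), automatic checks (9.8) and tabulation of missing data (9.7) also help. Stratification is the only analytic control for differential recording.
- *That the stratified analyses may never be run.* Only 9.9 is soft. The synopsis, 9.7 and item 10.3 of the ENCePP checklist all include them.
- *That the contrast must also be split by labelling era,* because 7.1 reports "introduction of warnings and precautions in the Summary of Product Characteristics (SmPC) for risk minimization measures to minimize the risk of serious infections". The protocol does not date that change. Such a split is a separate, optional analysis and no part of this point.

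**Conclusion.** The point holds. The conflict between 9.1 and 9.7, and the use of a single study-wide date, follow from the text. One step of reading is needed: 9.1 speaks of the start of the study but defines only the start of data collection, and the two are taken as the same date.

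The direction is also clear. Filing after-the-fact data as prospective tends to pull the strata together and hide under-recording. The amount is not known. The 13% to 38% (about 19 to 62 of 300 patient-years) rests on even accrual and the assumed treatment-time distributions; the 10% to 40% rests entirely on assumed site lags and applies to a site with that lag, not to the study as a whole. No study-size figure changes. This should be corrected, because the stratified comparison cannot otherwise be relied on to show a recording difference.

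**What to change.** Use one rule in the synopsis, 9.1 and 9.7:

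- Person-time and events are prospective only if dated after the site's activation or, for patients already on treatment then, after the patient's enrolment or identification date. Everything else is retrospective.
- Do not cut at the date of eCRF data entry. The synopsis ties entry of prospective data to the patient's last visit, so that cut could relabel patients followed prospectively as retrospective.
- Record the cut date, which 9.3 does not now list. Split each spanning patient's person-time and events at it, with delayed entry for the later segment in the Cox models.
- Bring 9.9 into line with the firm commitment in 9.7.

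The cost is wording, one recorded date, and a prospective stratum that shrinks by the person-time moved out of it, with somewhat wider intervals there.

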### **9.2. Setting**

The study will be conducted in the following countries (pending outcome of study feasibility): Australia, Austria, Belgium, France, Germany, Greece, Ireland, Italy, Portugal, Spain, Sweden, Switzerland and the United Kingdom.

Countries selected for this study include those in which an Early Access Program (EAP) for idelalisib in refractory FL patients has been running since the time of marketing authorisation (MA) for idelalisib. Additional countries without an active EAP were included based on the volume of idelalisib prescribing since the time of the MA. Sites within these countries will be selected based on whether they have been prescribing idelalisib for refractory FL patients in accordance with the approved product information for idelalisib. Final number of sites per country will depend on the available number of patients per site.

The study is expected to last 36 months from the start of data collection (Q1 2018) until submission of the CSR (Q4 2020).

Inclusion criteria:

- Adult patients (age ≥ 18) who were or are being treated for refractory FL according to the product information for idelalisib and treatment guidelines in routine clinical practice.

Exclusion criteria:

- Patients included in clinical trials on idelalisib within the timeframe of this study.

### 9.3. Variables

This is a non-interventional study. Only data available from routine medical care will be collected within the study. All variables collected will be identical in nature and independent of the method of data collection (retrospective/prospective).

#### At treatment initiation (baseline):

##### Demographics

- Gender, year of birth

##### Baseline Disease assessment

- Organ involvement
- Lymph nodes (bulky disease)
- Bone marrow involvement

##### Medical history

- Follicular Lymphoma History
  - Date of diagnosis
  - FL Stage 1, 2 or 3a
  - Ann Arbor disease stage
- ECOG Performance Status , if available

##### Treatment history:

- Prior treatment regimens for FL:
  - Drug names for each regimen
  - Number of cycles or duration that regimen administered
  - Reasons for discontinuation

Idelalisib treatment (start date, dose at baseline)

Co-medications:

- Current medications
- Name of medication
- Indication
- Start date or estimated duration on medication

Routine laboratory parameters and results (when available):

- Hemoglobin, erythrocyte count; total leukocytes, absolute neutrophil count, lymphocytes, monocytes, platelet count
- Serum chemistry including sodium, potassium, urea, uric acid, creatinine, lactate dehydrogenase (LDH)
- Liver function test: ALT, AST, ALP, GGT, total bilirubin, albumin, total protein

*During observation period (visits based on local clinical practice, collected retrospectively and prospectively):*

Collection of SAEs, SSRs, ADRs and SADR (see protocol section 11.1). Focus will be given to HOIs:

- any grade bowel perforation
- grade 3 diarrhoea and/or colitis
- any grade PML
- any grade pneumonitis
- grade 3 rash by MST
- infection (specifically grade 3 infection, grade 3 febrile neutropenia, grade 3 neutropenia, any grade CMV infection, and any grade PJP)
- Transaminase elevation
- SJS-TEN

#### Idelalisib treatment

- Change in idelalisib dose (date), including interruption of dosing and reason
- Co-medications (changes)

#### Routine laboratory parameters and results (when available):

- Hemoglobin, erythrocyte count; total leukocytes, absolute neutrophil count, lymphocytes, monocytes, platelet count
- Serum chemistry including sodium, potassium, urea, uric acid, creatinine, LDH
- Liver function test: ALT, AST, ALP, GGT, total bilirubin, albumin, total protein

#### Discontinuation (as defined by stopping treatment for more than 30 days) information

- Date and reason for discontinuation
- In case of death:
  - Date and cause of death

### **9.4. Data Sources**

The primary data source will be the patient's medical records. Review of electronic or paper medical records, data identification, abstraction and data transcription will be performed by trained site personnel. This will include all safety information that is entered into the patient's medical records (i.e., events and special situations). Data capture is electronic and therefore data collection will occur at time of data entry by the site. The investigator will seek to ensure data entry for retrospective data is conducted as close as possible to the identification of an eligible subject at the start of the study and prospective data as close as possible at the time of each patient's visit.

All data will be anonymised and collected for those patients meeting all eligibility criteria. Each patient will be identified by a unique eCRF generated subject identifier. For the retrospective data, medical record abstraction will be performed by internal study team members of the site, who will be trained on the abstraction method to ensure records are acceptable for review and inclusion in the study.

### **9.5. Study Size**

This study aims to include patients who have been or are currently being treated with idelalisib according to the product information and treatment guidelines for the treatment of refractory FL after marketing authorization in the EU (September 2014) and Australia (January 2015).

Prevalence data for iNHL in the EU are limited. HAEMACARE, a European cancer registry-based project on hematologic malignancies funded by the European Commission, provides European incidence rates but not prevalence data {Sant 2010}. Australian prevalence data could not be identified. The Decision Resources Group (<http://www.decisionresourcesgateway.com/index.aspx>) estimated a 10-year limited-duration prevalence for FL in 5 major EU countries (France, Germany, Italy, Spain, and United Kingdom) over the 2011-2021 forecast period based on cancer registry databases in the EU-5. The EU prevalence estimates for FL ranged from 1.4 (Spain) in 2011 to 3.1 (France) per 10,000 in 2015 (RMP, section 1.1.1.4.2).

Based on the pivotal studies 101-09, GS-US-313-0124 and GS-US-313-0125 the median treatment period is estimated to be 8 months, taking into account that studies GS-US-313-0124 and GS-US-313-0125 were terminated early. Thus, a retrospective timeframe of around 3 years and a prospective observation period of another 2.5 years allow data of approximately 300 patient-years to be collected.

A sample size of 300 patient-years is based on the chance to find a proportion of adverse events of 3.2% with a precision of 2%. The table below shows the relationship between various detectable single proportions of AEs and precision of the estimate.

Proportions found in studies 101-09, GS-US-313-0124 and GS-US-313-0125 were 1.4% ( Grade 3 diarrhea and/or colitis), 2.0% (( Grade 3 febrile neutropenia), 6.1% (( Grade 3 infection) and 8.1% (( Grade 3 rash).

Proportion of AEs	3.2%	5.2%	7.6%
Precision	0.02	0.025	0.03

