Rate	A measure of event occurrence, calculated by dividing the total number of events by the total amount of person-time within an exposure category
Risk	The proportion of a fixed cohort in which an outcome occurs during a specified period of time
Start of data collection	Date from which information on the first study subject is first recorded in the study dataset

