**Study Size:**

This study aims to include patients who have been or are currently being treated with idelalisib according to the product information and treatment guidelines in routine clinical practice for the treatment of refractory FL, after marketing authorisation in the EU (September 2014) and Australia (January 2015).

Assuming a median treatment period of 8 months, a retrospective timeframe of around 3 years and a prospective observation period of 2.5 years, it is expected that data of approximately 300 patient-years will be collected.

Patients will be identified and enrolled in Europe (pending outcome of study feasibility: Australia, Austria, Belgium, France, Germany, Greece, Ireland, Italy, Portugal, Spain, Sweden, Switzerland and the United Kingdom) and Australia.

---

**Data Analysis:** Continuous variables will be summarized by mean, standard deviation, median, lower quartile, upper quartile, minimum and maximum. Categorical variables will be summarized by number and percentage of patients in each categorical definition including 95% confidence intervals.

Multivariate Poisson regression analyses will be used to estimate adjusted rates of ADRs and SADR.

Multivariate Cox Proportional Hazard analyses will be used to model time-to-event data, and time to ADRs and SADR.

Kaplan Meier will be used to illustrate time-to-event analyses.

Stratified analyses will be used to account for potential behavioral changes of the site staff after the initiation of the study that might introduce bias between retrospective and prospective data collection.

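### Section 9.5 sizes the study at 300 patient-years using a precision that belongs to about 300 patients, and states neither a patient number nor which person-time counts

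*Protocol*

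**What the plan says.** Protocol section 9.5 states the size in person-time and justifies it by a proportion: "A sample size of 300 patient-years is based on the chance to find a proportion of adverse events of 3.2" per cent, with a precision of 2%. A table follows, introduced with "The table below shows the relationship between various detectable single proportions of AEs and precision of the estimate", which pairs 3.2% with 0.02, 5.2% with 0.025 and 7.6% with 0.03.

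The person-time is supported by the statement that "the median treatment period is estimated to be 8 months, taking into account that studies GS-US-313-0124 and GS-US-313-0125 were terminated early". From this, about 3 retrospective years and 2.5 prospective years are said to allow roughly 300 patient-years. The synopsis repeats that "it is expected that data of approximately 300 patient-years will be collected". Neither place gives a number of patients.

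Sections 9.1 and 11.1 set the collection window from treatment start (9.1) or prescription (11.1) until 6 months after idelalisib ends. Section 9.5 does not say whether those 6 months are part of the 300 patient-years.

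The glossary keeps two measures apart. A risk is a proportion of a fixed cohort. A rate is "calculated by dividing the total number of events by the total amount of person-time within an exposure category". Section 9.7 plans both: percentages of patients with 95% confidence intervals, and Poisson regression for rates. A comment in Annex 1 (its section 3) says that only incidence rates will be calculated.

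**The concern.** The precision of a proportion depends on the number of persons observed. The precision of a rate depends on the number of events, and so on person-time. Section 9.5 gives person-time and claims the precision of a proportion. That is justified only if one patient equals one patient-year on average, and nothing in the protocol says so. Its own durations, 8 months of treatment and a further 6 months of follow-up, do not point to 12 months.

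The study tests no hypothesis, so this precision statement is its only quantitative design claim. Without a patient number or a definition of the person-time, a reader cannot tell what precision the study will deliver for either measure.

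**Working it through.** **Inputs.** Proportions and half-widths come from the table in 9.5. The confidence level is not stated in 9.5; 95% two-sided is taken from 9.7 ("Categorical variables will be summarized descriptively by number and percentage of patients in each categorical definition including 95% confidence intervals"). Median treatment of 8 months is from 9.5 and the 6-month tail from 9.1 and 11.1.

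**1. Reproduce the table.** With the normal approximation for one proportion, n = 1.96² · p(1 − p) / d²:

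- 3.2%, d = 0.02: n = 297.5
- 5.2%, d = 0.025: n = 303.0
- 7.6%, d = 0.03: n = 299.7

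Conversely, at n = 300 persons the half-widths are 1.99, 2.51 and 3.00 points. The table is therefore the binomial precision for 300 persons.

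**2. Try a rate reading.** For a Poisson rate, person-time = 1.96² · rate / d². The three columns need 307, 320 and 324 patient-years. The first is close to 300, but the other two drift away, so only the binomial form fits all three. At exactly 300 patient-years the Poisson half-widths, 1.96 · √(rate/300), are 2.02, 2.58 and 3.12 per 100 patient-years. A 90% interval would need only about 210 persons and does not fit either.

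**3. Patients behind 300 patient-years.** N = 300 × 12 / (mean months per patient). The protocol gives a median and no mean, so two assumptions are shown: mean treatment of 8 months, and exponential treatment time with median 8 (mean 8 / ln 2 = 11.54 months). Half-widths are 1.96 · √(p(1 − p)/N), in percentage points.

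| Person-time counted | Mean months | N | at 3.2% | at 5.2% | at 7.6% |
|---|---|---|---|---|---|
| Treatment only, mean 8 | 8 | 450 | 1.63 | 2.05 | 2.45 |
| Treatment only, exponential | 11.54 | 312 | 1.95 | 2.46 | 2.94 |
| With full 6-month tail, mean 8 | 14 | 257 | 2.15 | 2.71 | 3.24 |
| With full 6-month tail, exponential | 17.54 | 205 | 2.41 | 3.04 | 3.63 |
| Table in 9.5 | 12 (implied) | 300 | 2.0 | 2.5 | 3.0 |

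**4. Break-even.** The 2-point half-width at 3.2% needs 297.5 persons, so it is met from 300 patient-years only if the average contribution is at most 300 × 12 / 297.5 = 12.1 months. With mean treatment of 8 months, that leaves room for an average tail of about 4.1 months. With a mean of 11.54 months it leaves about 0.6 month.

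**5. Person-time from 298 patients.** 298 × 8/12 = 199 patient-years, 298 × 11.54/12 = 287, 298 × 14/12 = 348, and 298 × 17.54/12 = 436.

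**The case against.** The strongest reply is that 9.5 derives its person-time from the treatment period alone and never mentions the tail. On that reading 300 patient-years is about 312 to 450 patients and every column of the table is met. This stands. A reader might infer that the study is undersized or misses its 2% target, but the documents do not support that as a flat statement. The miss needs the tail to be counted, a mean duration that the protocol does not give, and every patient completing the 6 months. Deaths and the end of data collection in Q3 2020 would shorten the tail and reduce the miss.

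A reader might also conclude that patient-years is the wrong unit throughout. It is not. It is the right unit for rates, which are a planned measure, and read as rates the table is off by only 0.02 to 0.12 per 100 patient-years. That closeness does not rescue the text, which speaks of proportions and matches the binomial form in all three columns.

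It is tempting to treat the four proportions quoted from earlier studies (1.4%, 2.0%, 6.1%, 8.1%) as 8-month risks. Section 9.5 gives no time window for them, so that cannot be said. Nor is it an error that the table omits these values, since it is illustrative.

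Finally, the study is descriptive, and Annex 1 answers No on whether sample size or power is estimated. That limits the consequences, but 9.5 still makes a sizing claim, and the claim should be correct.

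**Conclusion.** The point holds as a mismatch of units with a missing definition. The table in 9.5 is the 95% binomial precision for about 300 patients (297.5, 303.0, 299.7). It is attached to 300 patient-years with no patient number and no statement of whether post-treatment time counts, so the stated precision does not follow from the stated size.

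The identification of the table does not depend on any assumed duration, only on the 95% level used in 9.7. The direction of the effect does depend on such assumptions: under those shown, the number of patients behind the same figure runs from about 205 to 450. Even in the adverse cases the miss at 3.2% is modest, 0.15 to 0.41 points. The case for correcting it is that the only quantitative design figure is wrong as written and is cheap to put right.

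**What to change.** In section 9.5 and the synopsis:

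- State the number of patients behind the proportion precision (about 298 to 303 for the present table) and the patient-years they are expected to yield, with the mean duration assumed.
- Say whether those patient-years are on-treatment only or include the 6 months after discontinuation.
- Because incidence rates are a planned measure, add the Poisson precision at 300 patient-years: about 2.0, 2.6 and 3.1 per 100 patient-years at rates of 3.2, 5.2 and 7.6 per 100.

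The cost is one rewritten paragraph and table, with the synopsis aligned. No patients are added. The downside is that some figures may become slightly less favourable, depending on which person-time is meant.
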